STUDY PROTOCOL

THE EFFICACY AND SAFETY OF FIRST LINE ANTI-EPILEPTIC DRUGS (AEDs) AS SUBSTITUTION THERAPY FOR CHILDREN WITH DRUG RESISTANT EPILEPSY

Protocol Number 22-09-1097

ABSTRACT

Background: Drug resistant epilepsy occurs around 30% of children with epilepsy. It is the failure to get seizure-free after combining two or more anti-epileptic drugs whether first- or second-line ones. Previous studies focus on the efficacy and safety between the two groups whether as add-on or substitution therapy mostly in newly diagnosed epilepsy children. However, the study that investigate first line Anti-epileptic Drugs (AEDs) as substitution therapy compared to second-line ones particularly among drug resistant epilepsy children is still lack. **Design**: It is an open-label, randomized controlled trial, which will be conducted in three referral hospitals in Jakarta, Cipto Mangunkusumo, Harapan Kita, and Fatmawati Hospital, from November 2022 until April 2023. The data will be collected from electronic medical record consisting of demographic, clinical characteristics, and brain CT scan or brain MRI, and diary cards that record daily drug consumption and adverse drug reaction. Self-administered QOLCE-55 questionnaire is used to assess the quality of life of the children. Furthermore, there will be EEG and laboratory examination prior and after intervention. The data will be recorded on Case Report Form that is filled by the researcher. Ethics committee approval is obtained from The Ethics Committee of The Faculty of Medicine, University of Indonesia-Cipto Mangunkusumo Hospital. Research permits would be issued by each institution where the study will take place.

Sample: There will be 100 participants, divided into 2 groups, the intervention and control. Fifty children in the intervention group will be treated with first line AEDs as the substitution therapy, while the other 50 participants in the control group will get second-line AEDs. The sample size is calculated based on the difference proportion of two independent groups.

Duration of the study: The study will take 14 weeks as a whole that consists of 6 phases including baseline, initial, titration, maintenance, tapering-of, stopping and another maintenance phase.

Introduction

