This protocol is intended for a multicenter open label experimental, randomized controlled trial on the efficacy and safety of using first line AEDs as substitution therapy in childhood drug-resistant epilepsy. It will prospectively follow 100 children up during 14 weeks that consist of baseline, intervention, and post-intervention phases. While the intervention consists of 6 steps, as described at the Figure 1 below.

[figure not shown]

Figure 1. Timeline of the intervention phases

The study will be conducted at pediatric outpatient clinic of 3 referral hospitals in Jakarta, Cipto Mangunkusumo Hospital, Harapan Kita Hospital and Fatmawati Hospital. Children who are diagnosed with drug-resistant epilepsy receiving levetiracetam or topiramate will be enrolled in the study. Enrollment begins as soon as the research ethics committee approval is obtained from The Ethics Committee of The Faculty of Medicine, University of Indonesia-Cipto Mangunkusumo Hospital. The study will be closed after the last recruited patient has been followed up for the required 14 weeks.

All recruited children will be examined for monitoring at the hospital where the intervention is initiated. To avoid selection bias, all patients who met the inclusion criteria are divided into two groups, the intervention and control groups. Prospective participants and their parents will be provided with information related to the study. Patients will then fill out an information sheet containing demographic data, comorbidities, developmental history, school history, history of drug consumption, as well as history of seizures and patient complaints. All the data will be extracted and recorded on the case report form. Patients and their parents should be informed that participation is voluntary and they are free to withdraw from the study at any time. They should also be informed that refusal to participate or withdraw from the study will not affect the quality of treatment received. In the event of their withdrawal, it will be explained that the data collected so far is irrevocable, and we will seek consent to use such data in the final analysis if necessary.

Study procedure

Study procedures are depicted in Figure 2. The patients who are eligible for the study and have given their consents, will be enrolled, divided into 2 groups, the intervention and control, then start the 3-day baseline phase. In this phase, data such as demographic, clinical characteristic

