EEG recording results are categorized into:

- Normal: does not show of hypofunction/asymmetry/epileptiform waves
- Abnormal: shows a picture of hypofunction/asymmetry/epileptiform waves or a combination of 1 or more of these features

The subjects who show changes in their EEG are later grouped into groups of abnormal to normal or abnormalities that showed improvement. Abnormalities that show improvement, for example are hypofunction (slowing down) waves experience improvement or decreasing number of epileptiform waves.

Next, a proportion calculation is carried out in the form of the percentage to subjects who experience a change in the EEG and will be categorized into:

- Different : when a significant difference is shown in difference of proportion test of the group that reuses first line OAE line as substitution therapy and those that use standard therapy/
- Not different: when there is no significant difference is shown in difference of proportion test of the 2 groups.
- d. Difference in actual failure between the groups reusing first line OAE as substitution therapy and those taking standard therapy. Description of drug side effects in the form of frequency distribution and percentage of side effects in each group. Description of laboratory results in the form of frequency distribution and percentage of side effects in each group
- e. Factors contributing to decrease in seizure frequency (age, seizure onset, seizure type, family history of seizures, developmental delay, history of OAE, initial seizure frequency, initial EEG, structural brain abnormalities)

Sample size

The estimated sample size in this study was calculated using the different proportion formula for the 2 unpaired groups as follows ²⁹:

$$n1 = n2 = (\frac{Z_{\alpha}\sqrt{2PQ} + Z_{\beta}\sqrt{P1Q1 + P2Q2}}{P1 - P2})^{2}$$

Description:

n1 number of subjects who received the new drug (First Line OAE)

n2 number of subjects receiving standard drug (Second line OAE)

Alpha type one error (5%)

Zα alpha standard value 5% one-way hypothesis (1,96)

Beta type two error (20%)

Zβ beta default value 20% (0,84)

P2 proportion of decreased seizures on standard drugs (reference) for example 0.7

Q2
$$1-P2 = 1-0.7 = 0.3$$

P1-P2 difference in the proportion of reduced seizure that is considered significant between the new drug and the standard (defined by the researcher) for example 25% (0.25)

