P1 proportion of reduced seizure on the new drug (the proportion of reduced seizure on the standard drug in addition to the minimal difference that is considered significant)= 0.7 + 0.25 = 0.95

Q1
$$1 - P1 = 1 - 0.95 = 0.5$$

P
$$(P1 + P2) / 2 = (0.95 + 0.7) / 2 = 0.825$$

Q
$$1-P = 1-0.825 = 0.175$$

In this study, it was found that the proportion of seizure reduction on standard drugs was 70%.³⁰ Therefore the equation:

$$n1 = n2 = \left(\frac{1,96\sqrt{2(0,825)(0,175)} + 0,84\sqrt{(0,95)(0,5) + (0,7)(0,3)}}{0,25}\right)^2 = 49,56 = 50$$

$$n\ 2\ groups=100$$

Based on the formula above, 100 research subjects are required. An additional of 10% from the total number of subjects are needed as there is a possibility of those dropping out, therefore a total of 110 subjects are needed in this study.

Statistical Analysis

- 1. Analysis of differences in the proportion of responders (primary outcome), differences in EEG appearance (secondary outcome) in pediatric epilepsy patients who are resistant to the combination of second line OAE between those who reused first line OAE as substitution therapy and those who used standard therapy. Data type is categorical. Data is analyzed the Chi-square statistical test, if it does not meet the requirements then an alternative test is performed, known as Fisher's multiple test. The significance level (α) is 5% and the research confidence level is 80%. If p value ≤ α is obtained, this means H0 is rejected, which means that there is a difference seen in seizure frequency between reusing first line OAE as substitution therapy and standard therapy.
- 2. Analysis of differences in the mean quality of life with an unpaired T test if the data distribution is normal or Mann-Whitney if data distribution is not normal
- 3. To assess drug effectiveness, the analysis used was the difference in actual failure between those using first line OAE as substitution therapy and those using standard therapy (primary outcome). Formula:

$$ARR = CER - EER$$

CER: the incidence of increased seizure frequency in the standard therapy group ERR: the incidence of increased seizure frequency in the group in substitution therapy with 1st line OAE The increase in seizure frequency in this study shows therapy

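### The sample-size calculation takes 1 − 0.95 as 0.5 rather than 0.05, so the printed 50 per group does not follow from the plan's own inputs; its formula gives 36 evaluable per group

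*Combined protocol and SAP*

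**What the plan says.** The Sample size section uses the usual formula for two independent proportions. Its inputs are a 5% type I error with Z = 1.96, labelled "alpha standard value 5% one-way hypothesis (1,96"), a type II error given as "Beta type two error (20"%) with Z = 0.84, a response of 0.70 on the standard drug, and a difference of 0.25, so 0.95 on the new drug. The section then sets Q1, the complement of 0.95, to 0.5 and uses 0.5 again in the worked equation. The printed result is 49.56, rounded to 50 per group, followed by "Based on the formula above, 100 research subjects are required". Ten per cent is added for drop-out: "therefore a total of 110 subjects are needed in this study".

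Other sections bear on the same number:

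- The Abstract says "There will be 100 participants, divided into 2 groups, the intervention and control", and Study Design says "It will prospectively follow 100 children up during 14 weeks". Neither mentions 110.
- Statistical Analysis item 1 plans a chi-square test of responder proportions and adds "if it does not meet the requirements then an alternative test is performed", namely Fisher's test. It does not define the requirements.
- Items 1 and 6 of Statistical Analysis state that "the research confidence level is 80"%, next to a significance level of 5%.
- The text under item 3 of Statistical Analysis specifies intention-to-treat and per-protocol analyses. Under intention to treat, children who take no medication, are lost to follow-up or change group count as failures of their allocated group.

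**The concern.** One minus 0.95 is 0.05. Entering 0.5 makes the P1Q1 term ten times too large (0.475 instead of 0.0475), and that term feeds directly into the number of children. The number is the only product of the calculation, and it is the justification on which 100 children are said to be required. If it does not follow from the stated inputs, the stated type II error of 20% does not describe the design either, and the true basis for the trial's size is not on record.

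**Working it through.** **Inputs** (all from Sample size): Zα = 1.96, Zβ = 0.84, P1 = 0.95, P2 = 0.70, Q2 = 0.30, P = 0.825, Q = 0.175, P1 − P2 = 0.25.

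**Formula:** n per group = [(Zα√(2PQ) + Zβ√(P1Q1 + P2Q2)) / (P1 − P2)]².

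The first term is the same throughout: 1.96 × √(2 × 0.825 × 0.175) = 1.96 × 0.5374 = 1.0532.

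**1. Reproducing the printed figure (Q1 = 0.5)**

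- P1Q1 + P2Q2 = 0.475 + 0.21 = 0.685; 0.84 × √0.685 = 0.6952.
- n = [(1.0532 + 0.6952)/0.25]² = 48.91.
- Rounding each step to two decimals: 1.96 × 0.54 = 1.06 and 0.84 × 0.83 = 0.70, so (1.76/0.25)² = 7.04² = 49.56, exactly as printed.

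The gap between 48.91 and 49.56 is therefore explained by rounding and is not a second error.

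**2. Correct complement (Q1 = 0.05)**

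- P1Q1 + P2Q2 = 0.0475 + 0.21 = 0.2575; 0.84 × √0.2575 = 0.4263.
- n = [(1.0532 + 0.4263)/0.25]² = 35.02, so 36 per group, 72 in total.
- With the same two-decimal rounding: (1.06 + 0.43)/0.25 = 5.96, and 5.96² = 35.52, again 36.

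The printed size exceeds this by 50 − 36 = 14 per group, 28 in total.

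**3. Could another convention give 50?** With Q1 = 0.05 and 80% power: two-sided with continuity correction 43; one-sided 28; one-sided with continuity correction 36; unpooled variance 33. None gives 50. The one-sided 28 uses 1.645, so the 36 depends on reading 1.96 as what it is, the two-sided 5% value.

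**4. Power for 95% vs 70% among completers, two-sided 5%**

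Normal approximation: z = [0.25√n − 1.0532]/√0.2575.

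- n = 50: (1.7678 − 1.0532)/0.5074 = 1.408, power 92%.
- n = 36: (1.5000 − 1.0532)/0.5074 = 0.880, power 81%.

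The other two columns come from full enumeration of both binomials. The switching rule is an assumption: uncorrected chi-square, with Fisher's test when any expected count is below 5.

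| Completers per group | Normal approximation | Chi-square, switching to Fisher | Always Fisher |
|---|---|---|---|
| 36 | 81% | 82% | 76% |
| 50 | 92% | 95% | 90% |

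At 50 per group the assumed rule calls for Fisher's test in about 1% of samples. A 10% loss from 110 leaves 110 × 0.9 = 99; for 50 + 49 the first two columns are 92% and 94%.

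**5. Power if losses count as failures**

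Assumption: 10% lost in each arm, all counted as non-responders, 55 randomised per group.

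- Rates: 0.9 × 0.95 = 0.855 and 0.9 × 0.70 = 0.63; difference 0.225; mean 0.7425.
- 1.96 × √(2 × 0.7425 × 0.2575) = 1.2120; √(0.855 × 0.145 + 0.63 × 0.37) = 0.5976.
- z = (0.225 × √55 − 1.2120)/0.5976 = (1.6686 − 1.2120)/0.5976 = 0.764, power 78%. Enumeration with the same switching rule gives 79%.
- The plan's formula for these rates: [(1.2120 + 0.84 × 0.5976)/0.225]² = 58.03, so 59 per group.

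**The case against.** The best defence is that nothing in the conduct of the trial depends on the slip. It makes the trial larger, the tests and the significance level stay as they are, and the remedy keeps every planned child. That stands, and it limits the weight of the point. It does not make the printed figure right.

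A misread PDF is an unlikely explanation. The value 0.5 appears both in the line defining Q1 and in the equation, and only 0.5 leads to 49.56.

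A reader might go further in either of two directions, and the documents support neither.

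- *The trial is too big and could stop at 72.* The 36 per group counts evaluable children under a normal approximation. If Fisher's test were always used, 36 would give about 76% power, and counting losses as failures lowers power further.
- *The trial has 92–95% power and so cannot be underpowered.* This holds for completers only, and the upper end rests on an assumed trigger for Fisher's test that the plan does not define. Under the failure rule in Statistical Analysis, with 10% lost per arm, power is about 78–79%. That rule stands under item 3, and the plan does not say whether it also governs the responder comparison in item 1, so neither figure can be given alone.

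The 80% confidence level may simply mean the 80% power implied by a 20% type II error. That reading is plausible, so the phrase calls for clarification rather than plain deletion.

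**Conclusion.** The arithmetic error is certain. The plan's formula and stated inputs give 36 evaluable children per group (72 in total), not 50 (100), for a two-sided 5% test with 80% power at 95% vs 70%. The error is conservative before any loss to follow-up. No test, decision rule or enrolment target needs to change, so this is a correction of the record and not a threat to the trial's validity.

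The result takes the plan's 0.70 and 0.25 as given and does not vouch for them. For example, 90% vs 70% would need 62 per group by the same formula. The figure of about 78–79% also rests on the assumption of equal 10% losses in both arms, all counted as failures.

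**What to change.** In Sample size:

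- Set Q1 = 0.05, and use 0.95 × 0.05 in the worked equation.
- Label 1.96 as the two-sided 5% value.
- Report 35.02, so 36 evaluable per group (72 in total), as the number needed for 80% power.
- Keep the planned 110 enrolled (about 100 evaluable), and give those same two numbers in the Abstract and Study Design.
- State that 50 completers per group gives about 92% power for 95% vs 70% by the plan's normal approximation: about 90% if Fisher's test is always used, and about 95% for an uncorrected chi-square that switches to Fisher only when an expected count is below 5.
- Beside it, state that if losses count as failures and 10% are lost in each arm, the rates become 85.5% vs 63% and 55 randomised per group gives about 78–79% power.

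In Statistical Analysis items 1 and 6, reword the 80% confidence level as 80% power, if that is what is meant.

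The cost is one recalculation and wording. It needs no children beyond the 110 already stated and no change to the planned tests.

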This test will use 2 analyses known as intention to treat analysis and per-protocol analysis. Intention to treat analysis means that all research subjects who have been randomized are included in the analysis according to their initial allocation regardless of whether or not the subject is taking the drug/therapy being tested or a placebo, or whether these subjects died before taking the drug being tested. Subjects who did not

failure.

take medication, lost to follow-up, and who moved to another group, are considered failures of their original group.

Whereas per protocol analysis only includes subjects who complete the research to the end.

- 4. Analysis of the difference in time to achieve a decrease in seizure frequency with the chisquare test or if it does not meet the requirements, an alternative test is performed, namely the Mann-Whitney test
- 5. Analysis of clinical characteristics, side effects of OAE, and laboratory findings of complete blood count (hemoglobin, hematocrit, leukocytes, platelets, and type count), liver function (SGOT and SGPT), kidney function (urea and creatinine), and blood electrolytes (sodium, potassium, calcium, chloride) in pediatric epilepsy patients who are resistant to combination second OAE who re-use first line OAE as substitution therapy and who use standard therapy (secondary outcome). All existing data is processed and presented in a table consisting of mean and standard deviation or median and inter-quartile range, as well as frequency distribution.
- 6. Analyzing factors that affect the decrease in the frequency of late seizures (age, seizure onset, seizure type, family history of seizures, developmental delays, history of OAE, initial seizure frequency, initial EEG, brain structural abnormalities) in pediatric patients with resistant epilepsy combination of second line OAE who re-use first line OAE as substitution therapy (secondary outcome).

Data is categorical. Data is analyzed using Chi-square statistical test, if results do not meet the requirements then an alternative test will be performed, known as Fisher's multivariate test and further analyzed with multivariate test and logistic regression analysis. The significance level (α) is 5% and the research confidence level is 80%. Results will show statistically related if value of $p \le \alpha$ is obtained.

Ethics and dissemination

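### The 10% drop-out allowance fits an analysis that discards lost children, not the intention-to-treat rule that counts them as failures; if that rule governs the responder test, power is clearly under 80% at 100 children and marginal at 110

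*Combined protocol and SAP*

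**What the plan says.** The Sample size section assumes responder proportions of 0.70 on standard drugs ("P2 proportion of decreased seizures on standard drugs (reference) for example 0.7") and 0.95 on the new drug, with z-values of 1.96 and 0.84 (5% type one error, 20% type two error). It obtains 50 per group, 100 in all. It then states: "An additional of 10% from the total number of subjects are needed as there is a possibility of those dropping out", and arrives at 110. The Abstract gives a different total: "There will be 100 participants, divided into 2 groups, the intervention and control". The Study Design section also gives 100.

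Statistical Analysis, item 1, tests the responder proportions by chi-square, with a Fisher fallback. It names no analysis set. Item 3, which concerns the difference in failure and is also labelled primary, plans both an intention-to-treat and a per-protocol analysis. Under intention to treat every randomised child is analysed in the allocated arm, and those who did not "take medication, lost to follow-up, and who moved to another group, are considered failures of their original group". The per-protocol analysis keeps only children who finish the study. Neither is named as the main analysis.

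**The concern.** An allowance added to the sample size works by replacement: some children are lost, and enough remain for the planned comparison at the planned response rates. Where lost children are instead kept and scored as failures, the number analysed does not fall, but both response rates do. The difference between arms shrinks and the variance grows, and 10% more children need not make up for that. The allowance and the failure rule therefore describe two different analyses.

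At stake is whether the 80% power in the plan describes the analysis most readers would take as the main one. An arithmetic slip elsewhere in the same section adds a second risk: it enlarges the sample and so masks most of the loss. Correcting the slip alone would expose it.

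**Working it through.** **Inputs.** From the Sample size section: P1 = 0.95, P2 = 0.70, z-values 1.96 and 0.84, equal groups, 10% allowance. The plan labels 1.96 as one-way, but it is the two-sided 5% value and item 1 tests for a difference, so I work two-sided. My assumptions: the item 3 failure rule applies to the responder test, and loss is equal in both arms and unrelated to response.

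**1. The plan's own figure.** With 1 − P1 printed as 0.5:

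n = [(1.96·√(2·0.825·0.175) + 0.84·√(0.95·0.5 + 0.7·0.3)) / 0.25]² = 48.9

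The plan prints 49.56, rounded to 50. With the correct 1 − P1 = 0.05, the same formula gives 35.02, so 36 per group.

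**2. Power before any loss.** Solving the formula for power:

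power = Φ{ [(P1 − P2)·√n − 1.96·√(2PQ)] / √(P1(1 − P1) + P2(1 − P2)) }

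- n = 50: (1.768 − 1.053) / 0.507 = 1.408, power 92.0%
- n = 55: (1.854 − 1.053) / 0.507 = 1.578, power 94.3%

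The sample starts well above 80% only because of the slip in step 1.

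**3. 10% loss counted as failure.** 0.95 × 0.9 = 0.855 and 0.70 × 0.9 = 0.63. The difference is 0.225, P = 0.7425 and Q = 0.2575.

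- n = 50: (1.591 − 1.212) / 0.598 = 0.634, power 73.7%
- n = 55: (1.669 − 1.212) / 0.598 = 0.764, power 77.8%
- Needed for 80%: [(1.96·0.6184 + 0.84·0.5976) / 0.225]² = 58.03, so 59 per group (118 in all)

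**4. Over a range of loss.** Formula power, with exact enumeration of the uncorrected chi-square test in brackets:

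| Loss counted as failure | 100 children | 110 children |
|---|---|---|
| None | 92.0% (94.8%) | 94.3% (96.0%) |
| 5% | 83.3% (85.2%) | 86.7% (88.3%) |
| 10 of 110 (9.1%) | not applicable | 79.4% (80.4%) |
| 10% | 73.7% (74.9%) | 77.8% (78.6%) |
| 15% | 64.5% (65.1%) | 68.7% (69.4%) |

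At 110 children, formula power crosses 80% at about 8.8% loss.

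**5. If only the slip is corrected.** 36 per group plus 10% is 39.6, so 40. With 10% loss as failure: (1.423 − 1.212) / 0.598 = 0.353, power 63.8% (64.9%).

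**6. Per-protocol.** If 10 of 110 leave, 50 per arm remain at 0.95 against 0.70, with 92.0% power. For this set the allowance does its job.

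**The case against.** A reader might infer that the plan's intention-to-treat analysis is simply underpowered. The documents do not support that, for these reasons.

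- **Size at 110.** The allowance itself implies 10 lost of 110. Even if all are failures, power is 79.4% (80.4% exact). P1 and P2 rest on values the plan offers only as examples, so a gap of one or two points lies within the uncertainty of the inputs. This stands.
- **The 100-child figure.** With 100 enrolled, the allowance has not been applied at all, so part of that shortfall belongs to the conflict between 100 and 110. This stands, but 100 is what the Abstract and Study Design state.
- **Scope of the rule.** It is written for item 3, where failure means increased seizure frequency. This stands; the calculation is conditional. It is, however, the only intention-to-treat definition in the plan, and item 1 has none.
- **Per-protocol.** That analysis is also planned, and the allowance suits it. This stands, but the plan does not make it the main analysis.
- **Double counting.** The Study procedure section classes children whose intervention is ended for increased seizures as both non-responders and drop-outs, and it treats loss to follow-up separately. Such children already sit within the assumed non-response. If only half of the 10% are new failures, power at 110 is 86.7%. This stands.

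Two other choices move the figures. A truly one-sided 5% test would give 86.2% at 110 children and 10% loss. A continuity-corrected or Fisher test would give 71.8%, but expected failures of 55 × 0.2575 = 14.2 per arm make the fallback unlikely on the usual minimum of 5 (the plan does not state its requirement).

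**Conclusion.** The allowance and the intention-to-treat rule do not match. On the stated assumptions, 10% loss cuts the difference from 25 to 22.5 points and costs 94.3 − 77.8 = 16.5 points of power at 110 children. Most of that is absorbed by a margin the plan did not intend. The shortfall against 80% is clear at 100 children (73.7%) and marginal at 110 (77.8%, or 79.4% if 10 of 110 are lost). It becomes material at 110 only with heavier loss, about 69% at 15%.

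Equal loss matters greatly to these figures: at 110 children, 15% loss on first-line and 5% on standard drugs would give 39%, and the reverse 97%. The documents give no basis for either pattern. The 64–65% figure at 40 per group is not a defect of the present plan; it is a warning about correcting one error without the other.

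**What to change.** 1. In Statistical Analysis, item 1, state that the responder test uses intention to treat as its main analysis, with lost children counted as non-responders, and per-protocol as supportive. Say which of the drop-out categories in the Study procedure section fall under the rule.
2. In Sample size, correct 1 − P1 to 0.05.
3. Replace the 10% sentence with intention-to-treat power from the diluted rates over 5% to 15% loss: by the plan's formula, 83% down to 64% at 100 children and 87% down to 69% at 110.
4. Use one total throughout the document, 100 or 110.
5. Do not use the corrected 36 per group to reduce enrolment.

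The cost is wording. The stated intention-to-treat power may come out slightly below 80%, and no extra patients are required. Guaranteeing 80% at 10% loss would take 118 children; that is an option for the sponsor and not part of this request.
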